#### Fat Liver Content Change from Baseline:

The current sample size of 20 subjects per group should yield approximately 85% power to detect a treatment effect of at least ~ 5% with respect to the difference in the mean change from baseline between one of the JKB-121 treatment groups and placebo

#### ALT change from Baseline:

The current sample size of 20 subjects per group should yield approximately 73% power to detect a treatment effect of at least 30 U/L assuming a SE of 50 U/L ( $\alpha= 0.05$ ; two tailed; unpaired t-test). The SD of 50 U/L for the change from baseline endpoint was derived assuming SDs of 40 for the pre-and post-baseline measurements with a correlation of 0.25.

Sample size and power estimates have not been adjusted for multiple comparisons or multiple endpoints, dropouts or stratifications.

The analysis of each primary endpoint will be based on a linear model that incorporates the baseline measures as a covariate, the stratification factor and randomization treatment group. Pairwise comparisons of each active treatment group to control will be conducted vial linear contrasts.

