Other Parameters:	
The following measures of immunological profile will be explored in this study:
 
• Insulin resistance (HOMA-IR, insulin and glucose levels, HbA1c)• Lipid levels• Special laboratory functions panel include CK-18, adiponectin, leptin, ghrelin, TNF-α, TGF-β, hyaluronic acid, and MMP-2.

Statistical Considerations:

Sample Size Determination:

An approximate total of 60 subjects will be enrolled. Subjects will be randomized into three treatment groups in a ratio of Group 1 (5 mg twice daily): Group 2 (10 mg twice daily): Group 3 (placebo twice daily) = 1:1:1. No empirical power calculation is performed. The sample size is based on the best medical judgment.

The power to detect a difference between placebo and active treatment with respect to change from baseline in liver fat content and serum ALT has been determined for a sample size of 20 patients per arm to assess safety and potential efficacy. Fat quantification by MRI is very sensitive with as small as a 5% detectable change in fat quantification.

Further, since the endpoint is the change from baseline, plausible estimates of the degree of correlation between pre-and post-baseline measurements will be incorporated into the variance estimates. Given the wide range of results observed in the literature, several “what-if” scenarios were examined. As such, the current sample size was considered sufficient for the exploratory objectives of the study for the given range of plausible treatment effects and variance estimates. Due to the exploratory objects of the protocol, no adjustment for the two co-primary endpoints was made. Additionally, there will be no adjustments for multiple comparisons between the 3 treatment groups.

Assuming the observed difference between two treatment groups is 20%, then the 95% confidence interval for the true mean is given by (2.5%, 37.5%) with 20 subjects in each group.

Fat Liver Content Change from Baseline:

The current sample size of 20 subjects per group should yield approximately 85% power to detect a treatment effect of at least ~ 5% with respect to the difference in the mean change from baseline between one of the JKB-121 treatment groups and placebo

ALT change from Baseline:

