13. STATISTICAL CONSIDERATIONS

13.1 Sample Size Calculation

The study will need to screen approximately 100 subjects to enroll 60 patients with biopsy-proven NAFLD who meet the study inclusion / exclusion criteria. With 20 subjects per treatment group, the study will not be powered for efficacy assessment between the two doses. Based on precision analysis, the proposed sample size will provide the maximum error (defined as the half-way of the width of the 95% confidence interval for the difference (change in liver-biochemistry) between two doses (5 mg twice daily vs 10 mg twice daily dose) allowed.

Presuming the observed difference between two treatment groups is 20%, then the 95% confidence interval for the true mean is given by (2.5%, 37.5%) with 20 subjects in each group.

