Step 3: Endpoint would be calculated by averaging the values of Week 12 and Week 24. For each imputation, the ANCOVA model specified above would be performed to compare the change from baseline to Week 24 endpoint between JKB-121 5 mg group the placebo group, and between JKB-121 10 mg group and the placebo group.

Step 4: The procedure PROC MIANALYZE would be used with estimated statistics (“least-squares means”) and associated standard error from each simulation for overall testing results. The overall least-squares means, standard errors, 95% confidence intervals, and p-values would be reported.

The same analysis will be repeated for the mITT and Per Protocol Populations. Multiple imputation will not be performed for the Per Protocol Population; only subjects with both baseline and endpoint will be included in the analysis.

The percentage of fat content of the liver measured by MRI at Baseline and Week 24 will be summarized descriptively, as well as the change from baseline.

The same descriptive statistics and ANCOVA model as the primary efficacy endpoint will be applied to the percentage of fat content of the liver measured by MRI at Baseline and Week 12.

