### 6.9.2.2 Liver Function

The same descriptive statistics, ANCOVA model, and multiple imputation as the primary efficacy endpoint will be applied to serum aspartate aminotransferase (AST), ALT, and gamma-glutamyl transpeptidase (GGT) at each scheduled visit for the Full Analysis Set Population and the mITT Population.

As a sensitivity analysis, the change from baseline in AST, ALT, and GGT will be analyzed using a mixed-model repeated-measures (MMRM) ANCOVA model for the Full Analysis Set Population, implemented using SAS® Proc Mixed. The factors in the model will be diabetes stratum, treatment group, baseline value, visit, and the treatment group by visit interactions. An unstructured covariance matrix will be used (TYPE=UN). No imputation will be performed. The sample SAS code can be found below:

```
*****
Note:
  USUBJID = unique subject identifier
  TREATMENT = 0, (placebo), 1 (JKB-121 5 mg), 2 (JKB-121 10 mg)
  DIABSTAT = nondiabetic, diabetic
  VISIT = visit
  BASE = baseline value
  CHG = change from baseline to the specified visit
*****;
proc mixed;
  class USUBJID DIABSTAT TREATMENT BASE VISIT;
  model CHG = DIABSTAT TREATMENT BASE VISIT TREATMENT*VISIT;
  Repeated VISIT / TYPE=UN sub=USUBJID;
  lsmeans VISIT*TREATMENT / cl pdiff slice=VISIT;
run;
```

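### The stated 73% power for ALT change does not follow from its own inputs: the named unpaired t-test has about 46%, and the 50 U/L labelled an SE is an SD

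*SAP*

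**What the plan says.** The ALT paragraph of SAP 6.1 (Sample Size Determination), repeated in the protocol synopsis, states that 20 subjects per group "should yield approximately 73% power to detect a treatment effect of at least 30 U/L assuming a SE of 50 U/L". It names the test as a two-sided unpaired t-test at the 5% level.

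The next sentence accounts for the 50 U/L, now calling it an SD: "The SD of 50 U/L for the change from baseline endpoint was derived assuming SDs of 40 for the pre-and post-baseline measurements", with a pre/post correlation of 0.25. The paragraph then adds a caveat: "Sample size and power estimates have not been adjusted for multiple comparisons or multiple endpoints, dropouts or stratifications".

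The analysis planned for ALT is not that t-test. SAP 6.9.2.2 (Liver Function) says: "The same descriptive statistics, ANCOVA model, and multiple imputation as the primary efficacy endpoint will be applied to serum aspartate aminotransferase (AST), ALT" and GGT at each scheduled visit. The primary-endpoint model in SAP 6.9.1 has treatment, diabetes stratum and baseline value as terms. Step 3 of its imputation procedure says: "Endpoint would be calculated by averaging the values of Week 12 and Week 24".

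**The concern.** The power sentence gives everything needed to reproduce it: group size, difference, variability, significance level, sidedness and test. A standardised difference of 30/50 = 0.6 with 20 per group does not give power near 73% in a two-sample t-test.

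This is the only ALT power figure in either document. SAP 6.1 relies on such calculations when it says that power for liver fat and ALT was determined and that the sample size was considered sufficient. Someone reading a null ALT result would believe the trial had roughly a three-in-four chance of detecting 30 U/L, when the named test had less than an even chance. The SE label adds to the confusion: an SE of 50 U/L and an SD of 50 U/L describe very different trials.

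**Working it through.** **Inputs (SAP 6.1, ALT paragraph; same in the protocol synopsis).** n = 20 per group; difference 30 U/L; 50 U/L variability; two-sided alpha 0.05; unpaired t-test; pre and post SDs of 40 U/L; correlation 0.25.

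**1. Is 50 U/L an SD or an SE?** SD of change = sqrt(2 × 40² × (1 − 0.25)) = sqrt(2400) = 48.99 U/L, which rounds to 50. It is an SD. At SD 50 the standard error of the between-group difference is 50 × sqrt(2/20) = 15.8 U/L. If 50 U/L really were the standard error of the difference, the noncentrality would be 30/50 = 0.6 and power 9%.

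**2. Reproducing the stated figure with the named test.** Power is from the noncentral t with 38 degrees of freedom, with noncentrality 30 / (SD × sqrt(2/20)).

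| SD of change | SE of difference | Noncentrality | Power |
|---|---|---|---|
| 50 U/L | 15.81 | 1.897 | 45.6% |
| 48.99 U/L | 15.49 | 1.936 | 47.1% |

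The plan's 73% is not reproduced. The gap is 73 − 47.1 = 26 points or 73 − 45.6 = 27 points.

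**3. Does another reading give 73%?** Other between-group readings miss it by more than 2 points:

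- One-sided unpaired t-test: 58.7% (SD 50) or 60.1% (SD 48.99).
- Both doses pooled against placebo: 57.7% or 59.4%.
- At least one dose significant: 62.6% or 64.1%.
- Follow-up value only, SD 40: 63.7% two-sided, 75.3% one-sided.

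A one-sample t-test on 20 subjects (19 degrees of freedom) does fit. With noncentrality 30 / (SD / sqrt(20)), power is 72.1% at SD 50 (noncentrality 2.683) and 73.8% at SD 48.99 (noncentrality 2.739). That suggests a within-group formula was applied to a between-group comparison. The documents do not show the calculation, so this is an inference.

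**4. The planned ANCOVA, single Week 24 value, complete data.** Residual SD = 40 × sqrt(1 − 0.25²) = 38.73 U/L. SE of the difference = 38.73 × sqrt(2/20) = 12.25, so the noncentrality is 30/12.25 = 2.449. Power is 66.4% with 36 degrees of freedom and 67.2% with 55 (60 subjects less 5 model parameters). Simulations of the three-arm model, which allow for chance baseline imbalance, gave 65.5% to 66.3%. About 66% is a fair single figure.

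**5. The ANCOVA if Step 3 averaging were carried over to ALT.** Assume an SD of 40 at both visits, a correlation of 0.25 between baseline and each visit, and a 30 U/L effect at both visits. With between-visit correlation r, the residual variance of the Week 12/Week 24 mean is 1600 × (1 + r)/2 − 100. The documents give no r, so a range is shown (55 degrees of freedom).

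| Assumed r | Residual SD | Power |
|---|---|---|
| 0.75 | 36.06 | 73% |
| 0.50 | 33.17 | 80% |
| 0.25 | 30.00 | 87% |

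**The case against.** The strongest reply is that the t-test is not the planned analysis, so its power matters little. That is partly right. The planned ANCOVA is more powerful, and on a single Week 24 value it falls short of 73% by about 7 points rather than 26 to 27. A reader might go further and infer that the planned model cannot reach 73% either. The documents do not support that. SAP 6.9.2.2 carries the primary endpoint's imputation procedure over to ALT, and that procedure averages Weeks 12 and 24. The same sentence also refers to each scheduled visit, so it is unclear whether the averaging applies to ALT. If it does, step 5 shows that power could be 73% or more. None of this rescues the printed sentence, which names an unpaired t-test.

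A reader might also want power figures reduced for dropout. The documents give no dropout rate, plan multiple imputation, ask early discontinuers to return for end-of-treatment assessments, and already say that dropout was not allowed for. Completer-based figures would rest on the reader's own assumptions.

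A third temptation concerns the interval (2.5%, 37.5%) given for a 20% difference in the synopsis, protocol 13.1 and SAP 6.1. One could back-solve an SD from it and ask for that to be stated. But the interval equals the simple Wald interval for a single proportion of 20% with n = 20: 0.20 ± 1.96 × sqrt(0.2 × 0.8/20) = 0.20 ± 0.175, or (2.47%, 37.53%). No SD is needed to produce it, and a back-solved one would be an assumption found nowhere in the documents. All that can be said is that the basis of the interval is not stated.

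Finally, SAP 5.2 lists ALT change as a secondary endpoint, and SAP 6.1 calls the objectives exploratory, rests the sample size on medical judgment and even says that no empirical power calculation was done. This stands, and it limits the consequence.

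**Conclusion.** The point holds for the sentence as printed. With the stated inputs and the named test, power is about 46% (47% at the derived SD of 49.0 U/L), not 73%. The label SE should be SD in both documents; this follows from the plan's own next sentence and needs no outside assumption.

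The ANCOVA figure of about 66% is conditional. It assumes equal SDs of 40 U/L in all arms, a correlation of 0.25, one Week 24 ALT value per subject and no missing data. It should be reported with those conditions and not as proof that the planned analysis misses 73%. The one-sample explanation for the 73% is a lead for the authors, not a finding.

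This is a planning figure worth correcting, with limited consequence. It does not call the sample size, the tests or the endpoints into question.

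**What to change.** Keep 60 subjects and every planned test. In SAP 6.1 and the protocol synopsis, replace the ALT power sentence with:

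> With 20 subjects per group, a 30 U/L difference and an SD of 50 U/L for the change from baseline, an unpaired t-test (two-sided alpha 0.05) has about 46% power (47% at the derived SD of 49.0 U/L). A baseline-adjusted ANCOVA of a single Week 24 ALT value has about 66% power if the pre- and post-baseline SDs are 40 U/L, their correlation is 0.25 and all subjects have Week 24 data.

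This also removes the SE label. The authors should check whether the 73% came from a one-sample formula. For the interval (2.5%, 37.5%), at most state its basis or delete it in the three places where it appears.

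The cost is a text edit in two documents and a less favourable printed power. It adds no subjects and changes no analysis.

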## **6.2 Baseline, Endpoint, and Other Statistical Considerations**

The clinical statistical analyses will be performed by Medpace.

Baseline will be the measurement at Day 1. If missing, the last valid measurement on or prior to the first date administration of study medication will be used as baseline.

Unless specified otherwise, the order of the columns in descriptive summaries will be placebo, JKB-121 5 mg, JKB-121 10 mg, and total.

Descriptive statistics (n, mean, standard deviation, median, minimum, and maximum) will be used to summarize the continuous efficacy and safety data by treatment group. The count and frequency will be used to tabulate the categorical measurements.

Scheduled visits will be used according to their visit label. Unscheduled visits will be used if the scheduled visit is unavailable and the unscheduled visit is within the visit window. The window is defined as the halfway point between the previous (or subsequent) scheduled visit and the expected day of the visit.

Data will be used as it is reported. Last observation carried forward (LOCF) or multiple imputation may be used when specified.

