10.3.2 Screening Period (within 4 weeks before randomization)

Prior to performing any study procedures, an informed consent form will be reviewed and signed by each subject. Subjects will be screened within 4 weeks before starting study treatment to determine eligibility for participation in the study, unless otherwise noted below. Subjects who fail to meet eligibility due to an abnormal laboratory results (other than what is otherwise explained by NAFLD alone) may undergo retesting of the abnormal laboratory test during the screening window. This will be done at the discretion of the investigator and with prior approval from the Sponsor or Medical Monitor.

Sufficient time should be allowed for all screening laboratory studies to be resulted prior to scheduling subject for MRI testing. The following will be performed and documented at screening:

- Obtain subject screening number
- Obtain medical history and complete physical examination
- Record vital signs (blood pressure, heart rate, respiratory rate, body temperature)
- Record height, weight and body mass index
- Study pathologist to review screening liver biopsy (within 12 months of screening) for confirmation and staging of NASH as defined by NASH Clinical Research Network (NASH CRN) Grading and Staging System [28].
- MRI to be performed and study radiologist to review and confirm > 6% hepatic steatosis for inclusion
- Review concomitant medications that the subject has taken within 30 days prior to screening.
- Assess and record pre-dosing signs / symptoms
- Determine study eligibility
- Electrocardiogram
- Liver biopsy may be performed if subject has historical biopsy c/w NASH and biopsy is > 12 months of screening or subject at increased risk for NASH (increased liver enzymes with > 3 features of metabolic syndrome)

- Urinalysis
- Urine drug screen for amphetamine, cocaine and opiate drug screening
- Complete blood samples for:
 1. Complete blood count with differential
 2. Blood chemistry including: alanine aminotransferase (ALT), aspartate aminotransferase (AST), albumin, alkaline phosphatase, bicarbonate, blood urea nitrogen (BUN), calcium, chloride, creatinine, glucose, lactate dehydrogenase (LDH), magnesium, phosphorus, potassium, sodium, total and direct bilirubin, protein, uric acid, and gamma-glutamyl transferase (GGT).
 3. Fasting glucose and insulin level for HOMA-IR
 4. Glycosylated hemoglobin
 5. Prothrombin time and International normalized ratio (INR)

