11.2.2 Laboratory Safety Assessments

All laboratory tests following randomization will be performed by a study approved laboratory service. Samples will be drawn at sites and forwarded under appropriate conditions to the approved laboratory. The laboratory will communicate all test results to site study personnel. The Laboratory Assessing Physician will immediately notify sites of any values which lie outside pre-specified ranges. Screening samples, prior to initiation of study drug, may be analyzed at site.

Sites will be immediately notified of any test results that lie outside of pre-specified ranges. Site personnel will not be expected to transcribe results from the laboratory into the CRF, although abnormal results that are considered clinically significant should be entered in the CRF as adverse events. Screening assessments, prior to initiation of study drug, may be performed at sites. Sites are discouraged from performing additional routine investigations locally, but site personnel are permitted to perform any investigations at any time that may be necessary to safeguard patient welfare.

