## 6.9 Efficacy Analysis

### 6.9.1 Primary Efficacy Endpoint

The change from baseline at Week 24 of the percentage fat content of the liver measured by MRI will be analyzed by analysis of covariance (ANCOVA) in the Full Analysis Set Population with treatment group and diabetes stratum as factors and baseline MRI value as a covariate. The comparisons will be (1) between the response of the JKB-121 5 mg group and the response of the Placebo group and (2) between the response of the JKB-121 10 mg group and the response of the Placebo group. The least-squares means, standard errors, and 95% confidence intervals for each treatment group and for each comparison will be provided. The two-sided p-values testing for significance within treatment group change from baseline and comparisons between treatment groups will be presented. No multiple comparisons techniques will be applied. The sample SAS code can be found below:

```
*****
Note:
  TREATMENT = 0, (placebo), 1 (JKB-121 5 mg), 2 (JKB-121 10 mg)
  DIABSTAT = nondiabetic, diabetic
  BASE: baseline percentage fat content of the liver measured by MRI
  CHG: change from baseline to Week 24 in the percentage fat content of
       the liver measured by MRI
*****;
proc glm data=MRI;
  class TREATMENT DIABSTAT;
  model CHG = TREATMENT DIABSTAT BASE / ss1 ss3;
  means TREATMENT;
  lsmeans TREATMENT / cov stderr pdiff cl;
  estimate "JKB-121 5 mg : Placebo" TREATMENT -1 1 0;
  estimate "JKB-121 10 mg : Placebo" TREATMENT -1 0 1;
run;
```

The data and model residuals will be inspected for normality and homogeneity of variance, and a logarithmic transformation will be applied if necessary.

To handle missing results such as due to early termination, multiple imputation will be performed. The detailed steps are specified below.

Step 1: Prepare the data for multiple imputation. Since there is only one intermediate visit (Week 12) for MRI collection, the missing pattern would be monotone if endpoint values are not available.

Step 2: PROC MI would be used to impute the missing MRI values. The treatment, diabetes stratum, and MRI values at baseline and all available post-baseline visits would be included. The SAS code can be found as below:

```
PROC MI data=MRI out=MI_OUT nimpute=1000 seed=12345 minimum=0;  
  var TREATMENT DIABSTAT BASE WEEK12 WEEK24;  
  mcmc initial=em prior=jeffreys nbiter=200 niter=500 chain=single;  
run;
```

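### ALT, AST and GGT are adjusted only for the Day 1 value; adding the screening value already collected as a second covariate is a cheap, likely but not certain, gain for these secondary endpoints

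*SAP*

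**What the plan says.** SAP 6.2 fixes the baseline: "Baseline will be the measurement at Day 1". An earlier value serves only as a substitute: "If missing, the last valid measurement on or prior to the first date administration of study medication will be used as baseline".

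SAP 6.9.2.2 carries the primary model over to the enzymes: "The same descriptive statistics, ANCOVA model, and multiple imputation as the primary efficacy endpoint will be applied to serum aspartate aminotransferase (AST), ALT" and GGT. That model, in SAP 6.9.1, has "treatment group and diabetes stratum as factors and baseline MRI value as a covariate", so the enzyme version has one pre-treatment value. The sensitivity MMRM in 6.9.2.2 also has one baseline term.

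Protocol 10.3.2 lists the screening panel as "Blood chemistry including: alanine aminotransferase (ALT), aspartate aminotransferase (AST), albumin" and further analytes, with GGT at the end of the list. Protocol 10.3.3 repeats all three enzymes on Day 1. On where screening samples are assayed, Protocol 11.2.2 says: "Screening samples, prior to initiation of study drug, may be analyzed at site". Tests after randomisation go to a study-approved laboratory. Protocol 13.2 is looser than the SAP and allows baseline to come from Day 1 or from screening.

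**The concern.** One ALT reading is an imperfect measure of a subject's usual level. A second pre-randomisation reading exists for every enrolled subject, needs no extra visit, and can be used without risk of bias. With 20 subjects per arm and no allowance for dropout (SAP 6.1), precision for the enzyme endpoints has to come largely from the analysis. What is at stake is efficiency on secondary endpoints. The planned analysis is valid as it stands.

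**Working it through.** **Inputs from SAP 6.1 (ALT).** 20 per arm; difference 30 U/L; SD 40 U/L for each measurement; pre-post correlation r = 0.25; two-sided alpha 0.05; stated power about 73%.

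**Assumed.** The screening to Day 1 correlation, r12, appears in neither document, so it is varied. Values of r above 0.25 are also assumptions.

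**1. The plan's own figure.** SD of change = 40 × sqrt(2 × (1 − 0.25)) = 48.99, which the SAP rounds to 50. A two-sided unpaired t-test with SD 50 and 20 per arm has 45.6% power, or 47.1% with SD 48.99. The stated 73% is not reproduced. That is a separate matter; here the starting point is the ANCOVA.

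**2. Day 1 only.** Residual SD = 40 × sqrt(1 − r²) = 40 × sqrt(0.9375) = 38.73. With 60 subjects, three arms and one stratum term, 56 degrees of freedom remain before covariates. Chance imbalance in k covariates multiplies the contrast variance by 55/(55 − k). With k = 1, SE = 38.73 × sqrt(2/20 × 55/54) = 12.36, and power for 30 U/L on 55 df is 66.4%.

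**3. Day 1 plus screening.** If both values correlate equally with the outcome, R² = 2r²/(1 + r12). The imbalance factor becomes 55/53 and the error df 54. The second covariate therefore costs a factor (55/53)/(55/54) = 54/53 = 1.019, or about 1.9% of variance, before it gains anything.

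| r | r12 | Net variance change | Power, Day 1 only | Power, both |
|---|---|---|---|---|
| 0.25 | 0.25 | −2.2% | 66.4% | 67.4% |
| 0.25 | 0.5 | −0.4% | 66.4% | 66.6% |
| 0.25 | 0.7 | +0.7% | 66.4% | 66.1% |
| 0.25 | 0.9 | +1.5% | 66.4% | 65.8% |
| 0.5 | 0.5 | −9.4% | 76.0% | 80.0% |
| 0.5 | 0.7 | −4.1% | 76.0% | 77.7% |
| 0.5 | 0.8 | −1.9% | 76.0% | 76.7% |
| 0.6 | 0.6 | −12.4% | 82.3% | 86.9% |
| 0.6 | 0.7 | −8.2% | 82.3% | 85.3% |
| 0.6 | 0.8 | −4.5% | 82.3% | 83.9% |
| 0.7 | 0.8 | −9.0% | 89.8% | 92.3% |

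At r = 0.25 the break-even solves (1 − 0.125/(1 + r12)) × 54/53 = 0.9375, giving r12 of about 0.57. At r = 0.5 it is about 0.89. If screening carries nothing beyond Day 1 (its correlation with the outcome equals r × r12), the net change is +1.9% whatever r is.

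**4. Entry truncation.** Screening ALT is an entry criterion (above 40 U/L for women and 60 U/L for men, and not above 250 U/L), which narrows its range. Simulation with 60 subjects and 6,000 replicates, cutting screening at its mean (a deliberately severe assumption), gave:
- r = 0.25, r12 = 0.25: −2.2% becomes about +1%.
- r = 0.6, r12 = 0.7: −8.8% becomes −3.8%.
- r = 0.7, r12 = 0.8: −8.1% becomes −4.5%.

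Neither model showed bias. A further simulation used the 40/60/250 U/L limits, local-laboratory noise and varying response. It gave net reductions of about 0% to 7% when correlation decays with time and up to 15% when all visits are equally correlated, with no net loss.

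**The case against.** The strongest reply is that a single-baseline ANCOVA is standard, a pre-dose Day 1 value is a conventional baseline, and the trial is exploratory. At the only correlation the documents give, the extra covariate does almost nothing. All of that stands, and it is why this is an optional improvement and not an error.

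A reader might go further and call the gain free. The documents do not support that. The covariate costs about 1.9% of variance. Variance reductions of 3%, 11% and 16%, at r of about 0.22, 0.52 and 0.67, appear only if that cost is left out and screening and Day 1, at most 28 days apart, are taken to be no more alike than Day 1 and Week 24. Nor does r = 0.25 show that Day 1 is a noisy reading that a second one would repair. A low correlation over 24 weeks can also reflect real change or differing response, which no pre-treatment value recovers.

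Local assay across about 12 sites would weaken screening as a predictor. Entering it as a covariate keeps laboratory differences out of the endpoint but does not remove that weakening. For AST and GGT the documents give neither an SD nor a correlation, so no gain can be quantified.

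Against this, the downside is bounded at about 2% of variance, and the upside is several times larger if ALT is moderately stable within subjects.

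**Conclusion.** The point holds as a low-cost refinement. A pre-randomisation value of each enzyme is collected and left out of the models, and adding it is valid.

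At the plan's r = 0.25 the net effect is negligible: about −2% to +1.5% of variance, and at most about one power point. If r is 0.5 or more, the reduction for ALT is roughly 2% to 12%, about 1 to 4 power points and 4.6 in the most favourable tabulated row. Where it falls depends on r12, entry truncation and local-laboratory noise. It vanishes at r = 0.5 if r12 is about 0.9. These figures assume SD 40 U/L, 60 analysed subjects and equal correlation of the two pre-treatment values with the outcome.

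The change would not bring ALT power up to the stated 73% at r = 0.25. It does not touch the primary endpoint either: MRI has one scheduled scan before dosing, at screening.

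**What to change.** Before unblinding, amend SAP 6.9.2.2 as follows:
- Keep Day 1 as the baseline from which change is computed.
- Add the screening value of the same enzyme as a second continuous covariate in the ANCOVA, the MMRM and the imputation model.
- Do not average screening with Day 1. That would carry differences between site and study laboratories into the change score.
- Say what happens when Day 1 is missing, since the fallback in SAP 6.2 may then make the two covariates the same number.
- Keep the new covariate out of the CLASS statement of the MMRM code. BASE is listed there now, so baseline is treated as categorical. That is a separate fault which costs more degrees of freedom than this change could recover, and it can be corrected in the same edit.

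The cost is one line in each model, one degree of freedom, and making sure that screening values, including any assayed at site, are in the analysis database.
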